**Table 3: ARDS Severity Classification Post Day 1**

ARDS Severity	Variable	Criteria
Mild -1	PaO 2 /FiO 2 Ratio	200 mmHg < PaO 2 /FIO 2 ≤ 300 mmHg
Moderate-2	PaO 2 /FiO 2 Ratio	100 mmHg < PaO 2 /FIO 2 ≤ 200 mmHg
Severe-3	PaO 2 /FiO 2 Ratio	PaO 2 /FIO 2 ≤ 100 mmHg
Death-4	(Patient Status)	Yes/No

### ***5.3.3.6.3 Renal Function***

Fluids are monitored on a daily basis with the total input and output recorded (Day 1-28 / Last Day in ICU) and Fluid balance calculated (Input-Output).

The Last observation performed whether at Day 28 or earlier will be derived.

The change from baseline (Day 1 Pre-dose) will be calculated.

### ***5.3.3.7 Information from Externally Transferred Patients***

Observations recorded by site staff for patients who are externally transferred between Day 7 and Day 28 include: Total number of days spent in an ICU/Hospital, free of mechanical ventilation, free of organ failure, free of renal support or free of vasoactive support plus death date.

As this is a subset of patients these will only be numerically summarised. However, these data may contribute to the 'Days free' or 'Days spent' variable derivations and survival indicator (see Section 5.9.4, Appendix 4).

### ***5.3.3.8 Other Observations In The ICU***

Other observations recorded during Days 1-28 include Concomitant medications taken and any notable Procedures, Interventions, Surgeries and Diagnostics. These data will be categorically summarised and listed respectively.

## ***5.4 Efficacy Evaluations - Long Term/Extended Follow Up***

Long term follow up is performed first at Day 90 and then Day 180 after discharge from the ICU. This is followed by a further Extended follow up at Day 360. In the event of Early termination (on or before Day 28) no Long term follow up is performed.

Efficacy is assessed through Patient status assessments performed at Day 90, Day 180 and Day 360 with Respiratory and Neurological functioning and Quality of life (EQ-5D-3L) assessed at Day 180 and Day 360.

### ***5.4.1 Patient Status Assessments***

The Patient Status assessment records: Alive/Dead, Location of death (ICU/Hospital), Date of death, Location if alive (ICU/Hospital), Requirement for assisted ventilation at Day 90, 180 and 360 in a similar manner to those performed during Short Term Follow Up in the ICU.

These data will be categorically summarised.

### **5.4.2 Quality Of Life Evaluations**

General assessment of health is performed through a quality of life questionnaire (QOL). The EuroQol 5-Dimensions 3-Levels questionnaire (EQ-5D-3L) is administered at Day 1 Pre-dose, Day 180 and Day 360.

An EQ VAS score (ranging from 0-100) is measured (0= Worst imaginable health state, 100= Best imaginable health state) together with sub scores for Mobility, Self-care, Usual Activities, Pain/Discomfort and Anxiety/Depression. Each sub score ranges from 1 to 3 with 1 representing the best case and 3 the worst case.

The change from baseline (Day 1 Pre-dose) will be derived.

### **5.4.3. Respiratory and Neurological Assessments**

#### **5.4.3.1 Respiratory Function**

Respiration through the FEV-1 test is only assessed at Day 180 and Day 360 (and only if able to attend the hospital). This is a general test of pulmonary function. The FEV-1 is the volume exhaled as % of Forced Vital Capacity in 1 second.

Baseline measurement is not appropriate. These data will be numerically summarised.

#### **5.4.3.2 Neurological Function**

The Six-minute Walk Test (6MWT) is performed at Day 180 and Day 360. It evaluates global and integrated responses of all systems involved during exercise, including the pulmonary and cardiovascular systems, systemic circulation, peripheral circulation, blood and neuromuscular units and muscle metabolism.

The distance travelled over the 6 minute period on a flat, hard surface is recorded together with other potentially contributing factors. (Specific details of the procedure are given in the protocol Appendix II).

The test itself is performed according to the Respiratory Society/American Thoracic Society guidelines (Ref 11). The guidelines recommend that each test should be performed twice and the best result should be used. According to these guidelines this is usually the second result as it includes a 'learning effect'.

Details are recorded Pre-test, during the test and also post test for both Test One and Test Two.

Pre-test evaluations assess the Overall patient suitability to undergo the test (Absolute/Relative contraindications, ECG findings, Medication prescribed, Co morbidities present), Vital signs (Walking limitations, Systolic/Diastolic blood pressure, Heart rate, Oxygen required with flow rate and Peripheral capillary oxygen saturation(SpO2) and any other debilitating Symptoms (Dyspnoea and Fatigue as measured by the modified Borg scale (0-10)).

During the test the number of stops made by the patient and those requested by the Assessor are recorded.

After each test the Vital signs and any debilitating Symptoms are again recorded together with the Total distance walked (m) and the conditions under which the test was undertaken.

The Total distance walked (m) during Test One and Test Two on Day 180 and Day 360 will be numerically summarised together with the furthest distance walked during Tests One or Test Two. During this study, many patients have only performed the test once. Therefore, when only the first result is available this will also be used as the best result.

Baseline measurement is not appropriate. All other data will be numerically/categorically summarised as appropriate.

#### ***5.4.4 Study Completion / Unblinding***

After completion of the Short Term Follow Up period and as part of the Long Term/Extended Follow Up assessment period the completion of a Study Completion form is mandated at the end of study Day 180 or Day 360. Either the date of Withdrawal (if before Day 180 or Between Day 180 and Day 360) is recorded or the date of the End of Long Term Follow Up or Extended Follow Up is given.

All details of the reason for termination (including the primary reason) are given: Screen Failure, Protocol Violation, Non-Compliance, Lost to Follow-up, Retrospective Consent Not Given, Other Withdrawal of Consent, Investigator Decision, Death, Adverse Event (Non-Serious), Serious Adverse Event (Non-Fatal) or Other.

Any Unblinding performed (Yes/No) with Date of unblinding and Reasons are also recorded.

#### ***5.4.5 Exploratory Efficacy - Ventilation Free Survival At Day 90***

A protocol defined (Section 3.2.4) exploratory assessment of efficacy Ventilation Free Survival at Day 90 will be summarised. As daily assessments are not performed between completion of the Short Term Follow Up (Day 28) and Day 90, VFDsurv at Day 90 will be categorically classified as Dead, Alive-On Ventilator, Alive-Breathing Unassisted and summarised.

#### ***5.4.6 Secondary Efficacy - Mortality At Day 90***

Mortality (All causes) up to Day 90 will be derived from the recorded Date of Death (recorded as part of the Patient Status).

Investigators are also required to confirm mortality using the 'Death report' section of the eCRF. In the event of missing information, then patients are assumed alive and still 'at risk' at the time of assessment.

The cause of death detailed in the Death Report will be categorically summarised.

The date of death will also be used to produce Kaplan-Meier estimates and these will be displayed in plots to assess survival curves and median survival times. The number of patients ‘at risk’ at each assessment time will be superimposed. Information from the date of randomisation and for the entire follow up period will be taken into account. Patients who withdraw, are lost to follow-up, or are alive without the event occurring since the last follow-up will be considered right censored.

Mortality up to Day 180 and Day 360 will be evaluated as part of the Long Term and Extended Long Term Follow up assessments, respectively, and included as addendum reports (see Section 6.1.6 and 6.1.7).

### **5.5 Pharmacoeconomic Evaluations**

The total cost of treatment and care whilst patients are confined in the ICU (up to Day 28) will be derived from key individual patient efficacy measures and assigned unit costs for each measure.

UK Unit costs are considered representative and are given in Table 4.

Specific efficacy measures used are: Days free of organ failure, Days free of renal support, Days free of vasoactive support, Days free of mechanical ventilation, Number of ICU-free days, Number of days spent in hospital.

Individual patient need for these services will be determined in terms of days of use (subtracted from 28 for 'days free' or actual for 'days spent') and these will be multiplied by the daily costs to derive a total cost burden for each service and overall services.

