## **8.7 Pharmacoeconomics**

The expected incremental cost-effectiveness will be calculated for intravenous FP-1201-lyo compared with standard care in the treatment of patients with moderate or severe ARDS admitted to ICU in the study-related countries. Criteria that will be measured at D28 as part of the cost-effectiveness analyses in this study are:

- Days free of organ failure (D28 or last day in ICU if patient has left the ICU earlier than D28, or at withdrawal)
- Days free of renal support
- Days free of vasoactive support
- Days free of mechanical ventilation
- Number of ICU-free days

- Number of days in hospital

Details on the statistical analysis of these criteria and their role in the economic evaluation will be provided in the SAP.

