## 2. Objectives

The primary objective is to investigate the efficacy of FP-1201-lyo through improvement of the clinical course and outcome at Day 28. Efficacy is based on a composite measure of both survival and the need for mechanical ventilation (VFDsurv) in patients with moderate or severe ARDS.

Further objectives concern investigation of Safety, Secondary Short term efficacy and Long term efficacy, Pharmacodynamics including immunogenicity, as well as Pharmacoeconomics.

Safety of FP-1201-lyo is investigated through patient assessment and adverse event reporting

Secondary efficacy objectives, assessed during the Short Term Follow Up period, include the assessment of mortality (all causes) at Day 28, with further ICU based efficacy evaluations of Organ failure, Renal support, Vasoactive support and Mechanical ventilation (including pulmonary function through gas exchange PaO2/FiO2 ratio) followed by Time spent in intensive care unit (ICU) and Overall time spent in hospital.

Long term efficacy objectives, assessed during the Long Term and Extended Follow Up periods, include: investigation of survival (through Mortality Day 90, 180 and 360), requirement for mechanical ventilation (through Ventilation free survival), Quality of life (through EQ-5D-3L) and Organ functioning (through respiratory (FEV-1) and neurological (six minute walk test (6MWT))).

Pharmacodynamics objectives assessed during Short Term Follow Up period include the investigation of impact of FP-1201-lyo response through myxovirus resistance protein A (MxA), CD73 biomarker, Potential Inflammatory Markers (PIMs) and on neutralising antibodies to IFN beta-1a.

The Pharmacoeconomic value of FP-1201-lyo will be investigated through the total costs of standard treatment and care services used. These will be determined by application of unit costs to the key secondary efficacy outcome variables (Organ failure, Renal support, Vasoactive support, Mechanical ventilation and Stay in ICU/hospital).

A full description is provided in the protocol.

---

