**Table 4: Treatment And Care Costs Per Patient in the UK**

Support Service	Unit	Cost (£)
Organ Failure Support (SOFA)	Per Day	TBC
Renal Support	Per Day	TBC
Mechanical Ventilation	Per Day	TBC
Vasoactive Support	Per Day	TBC
Stay In ICU	Per Day	TBC
Stay In Hospital	Per Day	TBC

TBC: To Be Confirmed

The unit costs per patient will be provided to DML by the Sponsor prior to analysis, and will be based on the most current (2018) financial data available in the UK. Data for other countries may be displayed at a later date.

These data will be numerically summarised overall patients by Treatment group (FP-1201-lyo/Placebo) and Severity of ARDS (Moderate/Severe). However, to expedite the finalisation of

the Day 90 CSR, these summaries will be presented with the Day 180 and/or Day 360 long-term follow up reports and not at Day 90.

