### **6.2.6 Pharmacoeconomic Analysis**

Numerical summaries of overall costs and according to cost item for the UK will be by Treatment group (FP-1201-lyo/Placebo) and Severity of ARDS (Moderate/Severe) using the FAS population. NB: Separate summaries by other countries may be included later.

A cost-effectiveness analysis (Ref 9) to compare treatment with FP-1201-lyo to standard care (Placebo control) will involve an Analysis Of Variance (ANOVA) model. The total individual patient cost of treatment whilst in the ICU will be the response variable and Treatment group (FP-1201-lyo/Placebo), Severity of ARDS (Moderate/Severe) and Country (if available) will be included (without interactions) as fixed effect factors.

The total cost will be logarithmically transformed prior to analysis as the data distribution is likely to be truncated and positively skewed. The model fit and assumptions (particularly residuals) will be carefully assessed to ensure that the model is adequate and therefore provides reliable estimates.

Resulting model parameters for Treatment (FP-1201-lyo and Placebo) will be back transformed (exponentiated) to obtain geometric mean estimates (including 95%CI) of the total cost of each treatment and similar transformation of the treatment difference (FP-1201-lyo - Placebo) will allow expression of the difference in costs as a ratio (FP-1201-lyo relative to Placebo (%)) with 95% confidence limits.

In the event of model failure a non-parametric bootstrap procedure (Ref 10) will be substituted which involves repeated resampling from the available data to obtain estimates of the mean treatment costs together with 95% confidence intervals (using 2.5 and 97.5 percentiles from the resulting distribution).

A supplemental Incremental Cost Effectiveness Ratio (ICER) plot may also be presented for each Treatment group using the primary efficacy endpoint (VFDsurv) vs total cost of treatment for each individual patient.

This quadrant plot will identify both increasing and decreasing utility of the treatment cost with those of treatment efficacy

As discussed, these summaries will be presented with the Day 180 and/or Day 360 long-term follow up reports.

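### The cost-effectiveness analysis prices six support services but not FP-1201-lyo, so the incremental cost it reports is biased in the drug's favour

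*SAP*

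**What the plan says.** **Scope.** SAP 2 says that the pharmacoeconomic value of the drug "will be investigated through the total costs of standard treatment and care services used". It adds: "These will be determined by application of unit costs to the key secondary efficacy outcome variables".

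**Derivation.** SAP 5.5 says that the total cost "will be derived from key individual patient efficacy measures and assigned unit costs for each measure". It converts six efficacy measures into days of use, and "these will be multiplied by the daily costs to derive a total cost burden for each service and overall services". Table 4, titled "Treatment And Care Costs Per Patient in the UK", has six per-day rows: organ failure support, renal support, mechanical ventilation, vasoactive support, ICU stay and hospital stay. Every unit cost is still to be confirmed, and the sponsor is to supply the values before the analysis.

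**Analysis.** SAP 6.2.6 states: "A cost-effectiveness analysis (Ref 9) to compare treatment with FP-1201-lyo to standard care (Placebo control) will involve an Analysis Of Variance (ANOVA) model". The response is each patient's total cost in the ICU on the log scale. It is back-transformed to a ratio of FP-1201-lyo to placebo with 95% limits. If the model fails, bootstrap estimates of mean cost replace it. An optional ICER plot sets VFDsurv against the same total.

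**Purpose.** Protocol 8.7 says: "The expected incremental cost-effectiveness will be calculated for intravenous FP-1201-lyo compared with standard care in the treatment of patients". It lists the same six measures and leaves the detail to the SAP.

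**Data and timing.** SAP 5.2.2 describes a record of each daily administration on Days 1–6, output as Listing 16.2.1.22. The cost summaries are deferred to the Day 180 and/or Day 360 reports.

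**The concern.** The declared cost scope and the name given to the result do not match. The scope is routine care. The result is called cost-effectiveness of the drug against standard care, and an incremental cost has to contain the cost of the thing being added.

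This differs from leaving out an item that both arms share. The missing item falls on one arm only, so it goes wholly into the contrast being reported. Any fall in the use of care would appear as a saving, whatever the drug costs. A reader of the Day 180 or Day 360 report could take a cost ratio below 100%, or a favourable ICER plot, as evidence that giving FP-1201-lyo saves money. The analysis would have shown only that care other than the drug cost less.

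**Working it through.** The plan states no cost figure, so there is none to reproduce. The check is on the cost identity.

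**1. Inputs from the documents.** There are six costed items (SAP 5.5, Table 4) and no drug item. A full course is six doses, one a day (SAP 3). The reported contrast is a ratio of geometric means (SAP 6.2.6).

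**2. Planned cost and cost with the drug.** For patient *i*,

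- planned: C_i = Σ over six services of (days of use × daily unit cost)
- with the drug: C′_i = C_i + n_i × p

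Here n_i is the number of FP-1201-lyo doses received (0 to 6) and p is the price per dose. In the placebo arm n_i = 0, provided that no placebo patient is given an active vial by mistake.

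**3. Difference in mean cost.** The correct difference minus the planned difference equals (mean n in the active arm) × p. The prices below are assumptions, since the documents give none.

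| Price per dose (assumed) | Mean 5 doses | Mean 6 doses |
|---|---|---|
| £100 | £500 | £600 |
| £500 | £2,500 | £3,000 |
| £1,000 | £5,000 | £6,000 |

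The break-even price is (mean care saving) ÷ (mean doses). For example, a care saving of £2,500 at a mean of 5 doses breaks even at £2,500 ÷ 5 = £500 per dose. At any higher price the drug strategy costs more overall, yet the plan would report a saving.

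**4. Ratio of geometric means.** Let R be the planned ratio and R′ the ratio with the drug included. Then

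R′ / R = exp{ mean over the active arm of ln(1 + n_i p / C_i) }.

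Patients in the FAS have had at least one dose, so each term is positive for any p > 0 (mis-dosing aside). Therefore R is below R′. The direction needs no further assumption, but the size depends on the whole distribution of C_i.

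**5. Illustration on the planned scale.** The assumptions are equal care costs in both arms, log-normal with log-SD 0.6, and six doses for every active patient. The planned analysis would then centre on a ratio of 1.00 in every cell. With the drug included, simulation gives:

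| Price per dose (assumed) | Geometric mean care cost £20,000 | £40,000 |
|---|---|---|
| £100 | 1.04 | 1.02 |
| £500 | 1.17 | 1.09 |
| £1,000 | 1.34 | 1.17 |

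**6. ICER plot.** It uses the same total, so each active-arm point lies n_i × p too low on the cost axis, and placebo points do not move.

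**The case against.** **The scope is declared.** SAP 2 openly limits the evaluation to standard treatment and care services, and the protocol objective (2.2.3) asks only for an assessment of selected pharmacoeconomic parameters. A care-cost comparison satisfies both. A reader might infer that the plan cannot meet its stated objective, but the documents do not support that. What remains is the conflict between this scope and the cost-effectiveness and ICER terms in Protocol 8.7 and SAP 6.2.6.

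**Protocol 8.7 does not make the six measures the whole cost.** That is true. It passes the detail to the SAP, however, and the SAP adds nothing. The word *treatment* in SAP 5.5 and in the title of Table 4 does not help, because neither the derivation rule nor any row could carry a drug cost.

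**The size is unknown.** This stands. A reader might infer that the cost ratio is understated by course price divided by mean care cost. Guesses of £3,000 to £15,000 for the course and £30,000 to £60,000 for care would give 3,000 ÷ 60,000 = 5% to 15,000 ÷ 30,000 = 50%. That span reflects only the guesses, and the formula belongs to arithmetic means, whereas the plan reports geometric means.

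**Not every patient gets six doses.** A reader might also infer a shortfall equal to the full price of a course. This is exact only for patients given all six doses. SAP 7.2.1.1 plans to count those with fewer than six and fewer than four days of dosing.

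**An investigational drug may have no price.** None of the six services has a confirmed unit cost yet either. An unset price calls for a range, not for omission.

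**Unseen material.** SAP Appendix 4 and the table shells are not in the text available. A drug item there would answer the point, but Table 4 makes one unlikely.

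**Conclusion.** The point holds as a mismatch between what is costed and what is claimed. Followed as written, the plan gives an incremental cost for FP-1201-lyo that is too low at any positive price. The difference in mean cost is short by mean doses received times price per dose. The planned geometric-mean ratio is biased downwards by an amount that cannot be computed from the documents. The pound amounts and ratios in the working rest on assumed prices, care costs and doses, and show scale only.

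The consequence is confined to the pharmacoeconomic results. The primary endpoint, the testing hierarchy and the safety analyses are untouched. The ICER plot is optional, but the treatment-group cost model is not, and it has the same gap.

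**What to change.** Add a row to Table 4 for *FP-1201-lyo, per dose administered*. Charge it from the Days 1–6 administration record (Listing 16.2.1.22), and include it in the total cost, the cost model, the bootstrap fallback and any ICER plot. If no price is set at the time of analysis, report the results over a stated price range and give the break-even price.

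If the sponsor prefers not to cost the drug, relabel the analysis as a comparison of care costs excluding study drug. In that case, drop the ICER plot and the cost-effectiveness wording in SAP 6.2.6, and explain the departure from Protocol 8.7 in the report.

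Either route takes a few lines of SAP text and no new data. Because the analysis is deferred to the later reports, it need not delay the Day 90 report. The downside of the first route is a less favourable cost result.

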#### *8.5.2.2 Days Free of Organ Failure, Renal Support, Vasoactive Support, ICU Care and Days in Hospital*

Organ failure-free days are defined as the number of days in the first 28 days after the first dose of study drug that the patient is alive and free of organ failure with a SOFA score of zero.

ICU-free days are defined as the number of days from the time of ICU discharge to D28, assuming survival for at least two consecutive calendar days after ICU discharge and continued stay outside the ICU setting to D28. If a patient returns to the ICU and subsequently needs ICU admission to D28, ICU-free days will be counted from the end of the last period of ICU discharge to D28. A period of ICU admission lasting less than 24 hours in relation to a surgical procedure will not count in the calculation of ICU-free days. If a patient was in the ICU at D27 or dies prior to D28, ICU-free days will be zero. Patients transferred to another hospital or healthcare facility will be followed to D28 to assess this endpoint.

The statistical methods to be used for these secondary efficacy endpoints will be detailed in the SAP.

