### ***5.3.3.2 Days Free Of Mechanical Ventilation Evaluations***

The Total number of days free of Mechanical ventilation is derived from the Patient Status report recorded on each day during the 28 day period. Patients who die during this period will be assigned a value of zero. Defined rules are specified in Section 5.9.4, Appendix 4.

The definition used by site staff for unassisted breathing (UAB) and 'being ventilator free for the whole of the calendar day' as recorded in the CRF is given in the protocol.

This variable is not the same as the calculated Ventilation Free Days (VFD) endpoint which contributes to the VFDsurv primary efficacy endpoint as it requires 2 consecutive calendar days of UAB. If there are fewer than 2 consecutive days of UAB then VFD is assigned the value zero.

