#### **5.3.3.4. Length Of ICU 'Care Free' Stay/Hospital Stay**

Patient stay in the ICU and Hospital setting is also recorded daily in the Patient Status record. The Number of ICU care free days and the Number of days in hospital is derived from this information using defined rules and algorithms specified in Section 5.9.4, Appendix 4. Again patients who die during this period will be assigned a value of zero.

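### The cost analysis turns the zero score given to deaths into 28 days' use of five services and no hospital days, so costs for patients who die do not measure resource use

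*SAP*

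**What the plan says.** SAP Section 5.5 defines the quantity to be costed as "The total cost of treatment and care whilst patients are confined in the ICU (up to Day 28"). It builds the cost from six efficacy measures. Five are days-free scores (organ failure, renal support, vasoactive support, mechanical ventilation and ICU) and the sixth is days spent in hospital. Use is to be "determined in terms of days of use (subtracted from 28 for 'days free' or actual for 'days spent"), multiplied by a daily unit cost and summed.

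The same measures carry a penalty for death. For ventilation, SAP Section 5.3.3.2 states: "Patients who die during this period will be assigned a value of zero". Section 5.3.3.3 repeats this for organ failure, renal and vasoactive support. Section 5.3.3.4, which covers both ICU care-free days and days in hospital, adds: "Again patients who die during this period will be assigned a value of zero". For ICU-free days the protocol agrees (Section 8.5.2.2): "If a patient was in the ICU at D27 or dies prior to D28, ICU-free days will be zero".

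SAP Section 6.2.6 makes the resulting total the outcome of the cost model: "The total individual patient cost of treatment whilst in the ICU will be the response variable", and "The total cost will be logarithmically transformed prior to analysis". The result is a ratio of geometric mean costs with 95% limits. An incremental cost-effectiveness plot may be added. The unit costs in Table 4 are marked "TBC: To Be Confirmed".

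**The concern.** Zero for death is a reasonable worst score in a rank test of efficacy. It does not say how long a patient used a service. Subtracting it from 28 turns the penalty into a full 28 days of use, including days after death, although Section 5.5 limits the cost to care in the ICU. Sections 5.5, 6.2.6 and 7.2.6 make no exception for deaths and do not stop the count at death.

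The hospital item errs the other way. Zero days in hospital, used as it stands, means that the stay of a patient who dies is not charged. The same patient is then recorded with 28 ICU days and 0 hospital days, which cannot both be true.

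The trial is planned on a mortality difference, so under the sponsor's own assumption both errors fall unequally on the arms. The cost ratio and any cost-effectiveness plot would partly restate the mortality result in money. Protocol Section 8.7 commits the trial to an incremental cost-effectiveness calculation, so the error would reach a planned result.

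**Working it through.** The plan gives no cost figure to reproduce, because its unit costs are not set. The check applies the stated rule directly.

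**Inputs from the documents**
- Days of use = 28 − days-free score, or the value itself for hospital days (SAP 5.5).
- Score for a patient who dies in the 28-day period = 0 on all six measures (SAP 5.3.3.2 to 5.3.3.4).
- Planning D28 mortality: 30% control, 15% FP-1201-lyo (protocol Section 8.10). The difference is 0.30 − 0.15 = 0.15.

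**Assumptions, since the documents give no values**
- All deaths occur on day t, the same in both arms.
- r is the cost of a hospital day divided by the sum C of the five daily service costs.
- Patients who die stay in hospital until death.

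**One patient.** The rule charges 28 − 0 = 28 days per service, or 5 × 28 = 140 service-days, and 0 hospital days. A patient dying on day 3 can have used at most 5 × 3 = 15 service-days, so the overcharge is at least 125. For a death on day 14 it is at least 140 − 70 = 70, and on day 27 at least 140 − 135 = 5.

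**Between arms, in days per patient**
- Deaths contribute 28 × 0.30 = 8.4 days per service in the control arm and 28 × 0.15 = 4.2 in the FP-1201-lyo arm, a difference of 4.2.
- The artificial part is at least 0.15 × (28 − t). This lower bound takes patients who die to have used the service on every day alive. For a service they never used, the whole 4.2 days is artificial.
- The hospital item works in the opposite direction by 0.15 × t.
- The two cancel when r = (28 − t)/t.

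**On the planned scale.** The rule does not change survivors' costs. A death costs 28C under the rule and tC(1 + r) under actual use, if every service was used on every day alive. The mean log cost in an arm with mortality p rises by p × log[28/(t(1 + r))]. The ratio of FP-1201-lyo to placebo is therefore multiplied by [t(1 + r)/28]^0.15.

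| Assumed day of death t | 7 | 10 | 14 | 20 | 25 |
|---|---|---|---|---|---|
| Overcharge difference per service, at least (days) | 3.15 | 2.70 | 2.10 | 1.20 | 0.45 |
| Hospital difference, opposite direction (days) | 1.05 | 1.50 | 2.10 | 3.00 | 3.75 |
| Break-even r | 3.0 | 1.8 | 1.0 | 0.4 | 0.12 |
| Cost-ratio multiplier, r = 0 | 0.812 | 0.857 | 0.901 | 0.951 | 0.983 |
| Cost-ratio multiplier, r = 0.2 | 0.835 | 0.881 | 0.926 | 0.977 | 1.010 |
| Cost-ratio multiplier, r = 1 | 0.901 | 0.951 | 1.000 | 1.055 | 1.091 |

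At t = 10 and r = 0.2, (12/28)^0.15 = 0.881, an artificial saving of about 12%.

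**The case against.** **Hospital days.** The strongest objection is that Section 5.5 asks for actual days spent, so true hospital days were intended. Protocol Section 8.5.2.2 gives zero for death only to ICU-free days, and zero hospital days would be a good score rather than a penalty. This may well be the intention, but it is not what the SAP says. Section 5.3.3.4 names days in hospital and assigns zero to deaths, and in Section 5.5 the word actual only marks the contrast with subtracting from 28. If the objection is accepted, the offset disappears and the five-service error remains. The multiplier becomes [t(1 + r)/(28 + tr)]^0.15, which at r = 0.2 is 0.83, 0.87, 0.91, 0.96 and 0.99 for the same five days. The bias then favours the arm with fewer deaths at every t shown.

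**Appendix 4.** The derivation rules are said to be there, and it was not available for this review. A separate costing derivation cannot be ruled out. However, the body of the SAP states the zero rule, and its costing sections mention no exception.

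**Number of ICU days.** Section 7.2.3.2 lists this variable as an output, but Section 5.5 names ICU-free days as the cost input.

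**Size.** The figures are illustrative. With 18% mortality on FP-1201-lyo, as in some rows of protocol Table 6, the t = 10, r = 0.2 multiplier is (12/28)^0.12 = 0.90. With equal mortality and equal timing of death there is no between-arm bias. That limits what can be said about size, not whether the rule is wrong.

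**Data for the repair.** Protocol Section 7 restricts assessments up to D28 to patients in the ICU, whereas SAP Section 5.3.1 describes daily status to Day 28. Daily support data may therefore be missing for patients who die on a ward after leaving the ICU. This point stands, and the repair must allow for it.

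**Conclusion.** The concern holds. As written, each death by Day 28 is costed at 28 days of five services and no hospital stay, regardless of actual use. The five services are biased in favour of the arm with fewer deaths and the hospital item against it. At planning mortality, and over assumed days of death from 7 to 25, the service bias is at least 3.15 down to 0.45 days per patient per service. With r = 0.2, the cost ratio is multiplied by between 0.84 and 1.01.

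The net direction cannot be fixed, because the unit costs are unset and the timing of death is unknown. The sizes rest on the assumed t and r, and on the same t in both arms. The existence of the error rests only on the SAP text, subject to Appendix 4. The consequence is confined to the pharmacoeconomic objective. The cost analysis lies outside the testing hierarchy, and primary, mortality and safety conclusions are unaffected.

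**What to change.** Amend SAP Section 5.5 before unit costs are applied:

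- State that the death-penalised scores are for the efficacy rank tests only.
- For costing, count days actually spent on each service from the daily Patient Status record up to death, discharge or Day 28. Include actual ICU and hospital days for patients who die.
- For organ failure, which is not scored daily after Day 14, apply the interpolation rule of Section 5.3.3.3 without the zero for death, stopped at death. State how days between the last SOFA assessment and death are counted.
- For externally transferred patients, use reported days spent, or days alive since transfer (to death or Day 28) minus reported days free.
- State a rule for patients who die on a ward after ICU discharge, where daily support data may be absent.
- Check that Appendix 4, including its derivation of the number of ICU days, agrees with these rules.

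The cost is SAP wording and some programming, mostly on data already collected (daily status and date of death). The Day 90 report is not delayed, because Section 5.5 defers the cost summaries to the Day 180 and/or Day 360 reports.
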